To estimate the treatment effect for *longitudinally measured continuous outcomes*, the outcome will usually be defined as “change from baseline” (difference at follow-up visit minus baseline value). The treatment effect through follow-up will then be estimated with 95% confidence intervals using generalized estimating equations (GEE) with an indicator for treatment group, or, in the case of Gaussian responses, the corresponding mixed effects models with random effects for participants. To improve the model fit and reduce error variance, “visit number” (day) may be included as categorical variable in the model; alternatively, “time” may be included as continuous variable. Models will also be adjusted for the baseline values of the outcome variable.

Time-to-event outcomes will be summarized with Kaplan-Meier estimates for cumulative probabilities over time, and compared between treatment groups using stratified log-rank tests or Cox proportional hazards models, or their competing risk analogues.

In case “death” is a competing risk for the outcome (e.g., for time to hospital discharge), the following competing risk methods will be used:

- Aalen-Johannsen estimator for the cumulative incidence function (analogue to the Kaplan-Meier estimate)³
- Gray’s test with $\rho=0$ (analogue to the log-rank test)⁴
- Fine-Gray estimates and tests for the sub-distribution hazard ratio (analogue to the Cox proportional hazards model).^{5,6}

The proportional hazards assumption will be tested by adding an interaction term for time by treatment group to the model. The cumulative proportions of participants who experienced the event will also be compared at given time points (specified in secondary objectives, e.g., at 28 days); in this case, the cumulative proportions will be estimated using Kaplan-Meier estimates or the competing risks analogue, and/or as proportion of participants who reached the time point (e.g., time since randomization ≥ 28 days).

The **administrative follow-up time** is defined as the minimum of (cut date minus randomization date) or the analysis time period. For example, the analysis time period for the time to hospital discharge is 180 days, and the analysis time period for the important safety endpoint, the composite of *grade 3 and 4 events, SAEs, PSESEs, or death*, is 5 days or 28 days. The **administrative censoring date** is the earlier of the cut-date of the dataset or the randomization date plus analysis time period.

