For the closed report, enrollment and eligibility violations will be summarized by treatment group.

5 Baseline Characteristics

Baseline characteristics will be based on information collected on baseline and screening forms. Separate summaries will be provided for the Aviptadil and Remdesivir analysis cohorts.

For the open report, data will be pooled across treatment groups. In addition to the overall summaries, selected baseline characteristics will also be summarized by disease severity at study entry (2 strata, by use of *invasive mechanical ventilation or ECMO*).

For the closed report, baseline characteristics will be summarized by treatment group. For interim closed reports, baseline characteristics will usually be summarized by **modified intention-to-treat (mITT)**, for consistency with the safety summaries.

Unless noted otherwise, categorical variables will be summarized with the number and percentage (N, %) of participants in each category, and continuous variables will be summarized with the median and interquartile range (IQR); in the open report, in addition, the mean (SD) and range may be provided.

The following baseline characteristics will be reported:

- Number of participants with baseline data, overall and by study design stratum (N, %)
- Demographics
 - Age: distribution in categories 18-39, 40-49, 50-59, 60-69, 70-79, ≥ 80 years; and summary as continuous variable
 - Sex at birth
 - Ethnic group: Asian, Black, Latino/Hispanic, White, other
 - Country of enrollment

- Type of residence prior to COVID-19 (“home”)
- COVID-19 related characteristics
 - Duration of symptoms prior to enrollment
 - Level of care: non-ICU versus ICU
 - Respiratory support (4 categories: high-flow nasal cannula [HFNC], non-invasive ventilation [NIV], invasive mechanical ventilation without ECMO, or ECMO)
 - Time since initiation of oxygen support
 - Extent of lung infiltrates (3 categories: none, unilateral, bilateral)
 - ARDS (defined as bilateral lung infiltrates and SF ratio <315)
 - Receipt of SARS-CoV-2 vaccination (N, %)
 - Fully vaccinated at the onset of COVID-19 symptoms (\geq 14 days after the final vaccine dose [\geq 14 days since second dose, or since first dose if only one dose is required])
 - Type of vaccine
 - Received as part of a blinded clinical trial
- Vital signs (median [IQR] and categories)
 - Respiratory rate (categories: \leq 20 vs $>$ 20 breaths/minute)
 - Oxygen saturation (SpO2) (categories: <92%, 92-96%, $>$ 96%)

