The primary safety outcome of *grade 3 or 4 AEs, SAEs, PSESEs, or death through Day 5* includes potentially infusion-related outcomes; the analysis of the primary safety outcome is described in section 7. The current section describes safety analyses that are focused on the peri-infusion time period (i.e., during and within 2 hours after the infusion).

Peri-infusion signs and symptoms are reported as AEs (with grade and action taken) on eCRFs. Local labs are reported at baseline, Days 1 and 2 for all participants, and Days 3 and 5 if clinically available. Labs on Day 5 are reported for participants who are treated in the ICU.

Side effects of aviptadil observed in previous studies include:

- Hypotension with and without vasopressor
- Diarrhea
- Facial flushing
- Bradycardia
- Tachycardia

For the aviptadil versus placebo comparisons, incidence and management of hypotension in particular will be monitored in detail. Blood pressure is recorded prior to the start of the infusion and every 2 hours peri-infusion on each infusion day. Vasopressor use and dose are reported: prior to the start of the infusion, the highest dose peri-infusion, and the dose at 2 hours after the infusion.

The following data summaries will be provided overall for Days 0-2, and separately by day. Treatment groups will be compared using statistical methods described under “analysis principles” in section 3; comparisons will be stratified by disease severity at study entry (2 categories, by use of *invasive mechanical ventilation or ECMO*).

- Number and percentage of participants with infusion-related signs or symptoms (reported during the infusion or within 2 hours after the infusion), by type and grade, by type and grade cut-off (i.e., \geq grade 2, \geq grade 3, etc.), and by type and action taken.

Comments:

1. For aviptadil, **diarrhea is not included in the composite safety outcome** of incident grade 3 or 4 AEs, SAEs, PSESEs or death unless it is a SAE or leads to discontinuation of the infusion (for the day, or permanent discontinuation). Therefore, peri-infusion diarrhea AEs will be summarized in two ways: (1) as reported, and (2) restricted to diarrhea AEs that lead to discontinuation of the investigational agent.
2. Hypotension, diarrhea, facial flushing, bradycardia, and tachycardia are collected as part of the infusion-related signs and symptoms, and will be summarized by type and grade, and by type and action taken in response to the AE, as described above.

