Treatment groups will also be compared for the incidence of PSESEs using time-to-event methods; because death is a PSESE, the overall comparison will use Cox proportional hazards models, while comparisons for individual components will use the Fine-Gray model to account for the competing risk of death. Models will be stratified by disease severity at study entry (*invasive mechanical ventilation or ECMO* vs. neither) if event numbers permit.

- Treatment groups will be compared for incidence of a composite of cardiovascular and thromboembolic events, a subset of the organ failure outcome (items b1, e2, e3, and f2 in [Appendix B](#)). Time-to-event methods will be used that take into account the competing risk of death (as described in section 3, using Aalen-Johansen estimates for the cumulative incidence functions, and Gray's and Fine-Gray's methods to compare treatment groups and estimate the sub-hazard ratio).
- **Subgroup analyses:** The impact of study arm on the primary safety outcome (composite of grade 3 or 4 events, SAEs, PSESEs, or death through Day 5) and other important safety outcomes will be assessed for subgroups defined by baseline characteristics, including demographics, duration of symptoms at enrollment, baseline classification of “home”, clinical history and presentation (including disease severity at study entry), use of concomitant medications, and, if available, baseline levels of antibodies, antigen and viral RNA; tests for homogeneity of the treatment effect across subgroups will be carried out. Outcomes and methods for subgroup analyses are described in detail in section 8.5.
- Treatment groups will be compared for mean changes in laboratory test values from baseline to Day 3, and for incidence of grade 3 and 4 laboratory abnormalities at Day 3 (new abnormality or increase in grade). Laboratory tests include the basic metabolic panel (BMP), complete blood count (CBC) with differential, international normalizing ratio (INR), D-dimer, AST, ALT, and bilirubin. Statistical methods are described in section 3. Biomarkers will be log-transformed as needed.
 - For all participants, these biomarkers will be determined locally on Days 0, 1, and 2. Treatment groups will be compared for mean changes from baseline through

Day 2, overall using longitudinal models, and pointwise at Days 1 and 2 using ANCOVA models; models will be adjusted for baseline biomarker levels.

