- For participants who are in the ICU on Day 5, these biomarkers are also collected on Day 5. For this cohort, trajectories of mean biomarker values will be described, and treatment groups will be compared for mean changes in biomarker values from baseline through Day 5.
- For renal function lab tests, participants who are on dialysis at study entry will be excluded.

- Pregnancy outcomes will be summarized.

Listings of SAEs, PSESEs, incident grade 3 and 4 AEs, UPs, SUSARs, and deaths (with cause of death) by treatment group will be provided at each DSMB meeting, with new events highlighted. The listings will include important baseline characteristics, such as age, sex, and level of respiratory support at study entry.

Further safety assessments may be considered.

Concomitant medication use is collected at baseline, and daily through Day 7; additionally, any use between Days 8 and 14, and use on Day 28 is reported. Vasopressor use is reported daily for Days 0-14. The following categories of concomitant medications will be summarized by treatment group:

- Corticosteroid use (daily for Days 0-7, any use through Day 14)
- Vasopressor use (daily for Days 0-14)
- Anticoagulation and antiplatelet therapy, by type
- COVID-19 treatments other than corticosteroids, by type
- Other summaries will be provided by request of the DSMB or study leadership.

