¹ Screening must be performed within 24 hours of randomization.

² These laboratory evaluations will only be performed as study procedures if they are unavailable clinically on that study day

³ Duration of study drug administration may vary by investigational agent; the sample provided here is for 3 successive days. Where the duration of study drug administration

varies from this schedule, the duration will be specified in the relevant agent-specific Appendix.

⁴ The Day 14 visit will record values for Days 8–14.

⁵ These will be not be collected after hospital discharge.

⁶ These laboratory assessments will only include clinically available results

⁷ It is acceptable to perform the Day 3 draw on Day 4.

⁸ The Day-5 draw will occur only among patients who remain in the intensive care unit (ICU) or equivalent. It is acceptable to perform the Day 5 draw on Day 5 \pm 1, but the Day 3 and Day 5 draws can not both be performed on Day 4.

⁹ Includes telephone administration of the Euro-QOL-5D-5L instrument.

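### Arms are compared on Day 5 laboratory change only among participants in the ICU on Day 5, a post-randomisation state, so the comparison is not protected by randomisation and can create, shrink or hide a difference

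*SAP*

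**What the plan says.** SAP section 7.1 sets out three layers of laboratory comparison.

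- **Days 1 and 2:** "For all participants, these biomarkers will be determined locally on Days 0, 1, and 2". Arms are compared longitudinally and at each day, with adjustment for the baseline level.
- **Day 3:** "Treatment groups will be compared for mean changes in laboratory test values from baseline to Day 3". New or worsened grade 3 and 4 abnormalities are compared as well. No ICU condition is attached, although section 6.1 says Day 3 results are reported only if clinically available.
- **Day 5:** "For participants who are in the ICU on Day 5, these biomarkers are also collected on Day 5". For this group the SAP describes trajectories and adds that "treatment groups will be compared for mean changes in biomarker values from baseline through Day 5".

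The ICU restriction at Day 5 is deliberate and appears elsewhere. Section 6.1 says: "Labs on Day 5 are reported for participants who are treated in the ICU". A footnote to the schedule in Appendix E, taken from the protocol, says: "The Day-5 draw will occur only among patients who remain in the intensive care unit (ICU) or equivalent".

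Section 7.1 stratifies its models by disease severity at entry (invasive ventilation or ECMO, versus neither). For longitudinal continuous outcomes section 3 adds: "Models will also be adjusted for the baseline values of the outcome variable". The SAP attaches no caveat, selection adjustment or sensitivity analysis to the Day 5 comparison.

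**The concern.** A participant enters the Day 5 comparison only by being alive and in intensive care several days after randomisation. For aviptadil that is also after the three infusion days (Days 0 to 2). Both agents are being tested because they may change recovery and death, so the trial's own hypotheses allow treatment to alter who is sampled. Not everyone need start in the ICU either: section 5 tabulates "Level of care: non-ICU versus ICU" as a baseline characteristic.

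If an agent moves less ill patients out of the ICU sooner, those who stay in its arm are sicker on average. The agent then looks worse on any marker that rises with severity, such as D-dimer or INR. If it delays discharge, the bias runs the other way and could hide toxicity. Adjusting for baseline values does not cure this, because the selection acts on severity that develops after baseline.

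The SAP applies the principle elsewhere. Subgroups are defined at baseline (sections 7.1 and 8.5), and sections 3, 8.5 and 9 warn where a comparison is not protected by randomisation. The Day 5 comparison carries no such warning. Section 7 analyses go to the DSMB in the closed reports (section 2), and section 7.2 says safety data on aviptadil are limited, so a misleading laboratory signal would be seen by the body that judges safety.

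**Working it through.** **Plan's own figure.** The SAP gives none for this comparison. The only design figure used is 320 per group (section 1.4). Safety analyses are by mITT, so the actual number may be smaller.

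**Assumed, not in the documents.** The share in the ICU on Day 5 in each arm (p_C control, p_T drug) and the correlation r between the biomarker and the latent severity that keeps a patient in the ICU. The model also assumes normal severity, no drug effect on the biomarker, and no deaths.

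**Step 1: closed form.** Let c = Φ⁻¹(1 − p) and λ(p) = φ(c)/p, the mean severity of those in the ICU. Then:

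- false difference Δ = r[λ(p_T) − λ(p_C)]
- variance within an arm v = 1 − r²λ(λ − c)
- SE = √[v_C/(320 p_C) + v_T/(320 p_T)]
- rejection = Φ(−1.96 + Δ/SE) + Φ(−1.96 − Δ/SE)

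The values are λ(0.70) = 0.4967, λ(0.65) = 0.5698 and λ(0.60) = 0.6439.

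For 70% versus 60% and r = 0.5:

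- Δ = 0.5 × (0.6439 − 0.4967) = 0.0736 SD
- SE = √(0.8732/224 + 0.8556/192) = 0.0914
- Δ/SE = 0.805, so rejection is 12.7%

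| ICU share, control vs drug | r | Δ (SD) | Rejection |
|---|---|---|---|
| 70% vs 60% | 0.5 | 0.074 | 12.7% |
| 70% vs 60% | 0.3 | 0.044 | 7.5% |
| 70% vs 65% | 0.5 | 0.037 | 6.9% |
| 70% vs 65% | 0.3 | 0.022 | 5.6% |
| 70% vs 70% | any | 0 | 5.0% |

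Simulating the same model (20,000 trials per setting) gave 12.6% to 12.7%, 7.5% to 7.7% and 6.8% for the first three rows, and 4.9% for equal shares.

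**Step 2: add baseline adjustment.** A simulated ANCOVA on the baseline biomarker (4,000 trials, Monte Carlo error about 0.7 points at 5%), with r defined given baseline, gave these results for 70% versus 60%:

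- r = 0.3: 0.039 SD and 8.5%
- r = 0.5: 0.064 SD and 12.4%
- r = 0: 4.8%

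Equal shares of 80% gave 4.8% to 5.3%. Baseline adjustment does not remove the bias.

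**Step 3: add the severity stratum.** Section 7.1 requires it. I assumed 40% prevalence and a correlation of 0.6 to 0.8 between the stratum's underlying scale and latent severity. For 70% versus 60% the results fall to about 0.05 to 0.06 SD and 9% to 11% (r = 0.5), and about 0.03 to 0.04 SD and 6.4% to 7% (r = 0.3). The bias shrinks but stays.

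**Step 4: a different mechanism.** Suppose treatment lowers severity itself, enough to move ICU occupancy from 70% to 60%, so the biomarker falls too. The cut-offs are −0.5244 and −0.2533, so severity shifts by −0.271. With r = 0.5:

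- in all participants the true difference is 0.5 × (−0.271) = −0.135 SD
- among those in the ICU it is 0.5 × (−0.271 + 0.6439 − 0.4967) = −0.06 SD

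Less than half of a real benefit would be seen.

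**The case against.** **The lead scenario is large.** 70% versus 60% in the ICU is an odds ratio of (0.70/0.30)/(0.60/0.40) = 1.56 by Day 5. The design alternative is 1.5 for recovery at Day 90 (section 1.4). The milder 70% versus 65% is (0.70/0.30)/(0.65/0.35) = 1.26. This stands: the 13% end of the range is an upper-range illustration, not a forecast.

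**The plan's stratification reduces the effect.** This also stands, as step 3 shows.

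**The direction is not fixed.** A reader might infer that the comparison would make a beneficial drug look toxic. The documents do not support that as the expected result. It needs treatment to change ICU stay without changing the severity behind the biomarker. If severity itself falls, a real benefit is attenuated instead. Death is not modelled; it removes the sickest, and its effect on the bias is untested.

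**Sound safety evidence is already planned.** A reader might also infer that the trial's safety conclusions or stopping decisions are compromised. They are not. The primary safety endpoint through Day 5 includes death and uses the whole mITT cohort. Deaths by Day 5 are tabulated by arm, and Day 1 and 2 laboratory values are compared in all participants (all in section 7.1). Safety monitoring rests on the totality of evidence (section 10.1), and the stopping boundaries use mortality (section 10.2). No decision rule uses the Day 5 laboratory test.

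**The sampling comes from the protocol schedule.** True. SAP wording cannot supply Day 5 values for those not drawn; it can change only how the available values are used and labelled.

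None of this makes the ICU group a randomised comparison.

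**Conclusion.** The point holds, as a minor one. Section 7.1 plans a between-arm comparison in a group formed after randomisation, and nothing in the SAP removes or flags the selection. The comparison can give a false difference, or attenuate or mask a true one.

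The bias needs two conditions: ICU membership on Day 5 must differ by arm because of treatment, and the biomarker must share causes with ICU stay. If either is absent, the test keeps its 5% level. Under the assumptions above the false difference is a few hundredths of an SD, and rejection ranges from just above 5% to about 13%. The low end belongs to small differences in ICU share and to severity-adjusted models. The high end should not be quoted as the size of the problem, because its inputs are not in the documents.

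**What to change.** Amend the Day 5 item in SAP section 7.1 as follows.

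1. Present Day 5 values and changes from baseline descriptively by arm, with no between-arm test.
2. Alongside, report by arm the number and percent who on Day 5 are in the ICU, alive and out of the ICU, and dead. No post-baseline ICU count by arm is visible in the present plan; ICU status must already be known to define the cohort.
3. State that the Day 5 cohort is defined after randomisation and that differences between arms within it are not protected by randomisation.
4. Rest laboratory inference on the all-participant Day 1 and 2 comparisons. Leave the planned Day 3 comparison unchanged; nothing here argues for dropping it.

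A longitudinal model that treats unsampled Day 5 values as missing is a weaker option. It needs data to be missing at random given earlier values, and it implies Day 5 values for participants who have died. Restricting to participants in the ICU at baseline would not solve the problem either, since leaving the ICU still follows randomisation.

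The cost is the supportive Day 5 laboratory tests. No new data are needed, and the primary efficacy and primary safety analyses do not change.

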7.2 Additional Safety Analyses for the Aviptadil Cohort

Limited safety data are available for aviptadil. Therefore, infusion reactions to aviptadil will be carefully monitored. Side effects of aviptadil observed in previous studies include:

- Hypotension with and without vasopressor
- Diarrhea
- Facial flushing
- Bradycardia
- Tachycardia

Data summaries that address these potential side effects during or within 2 hours after the infusion are described in section 6.1, under “Safety”.

In addition, the aviptadil and placebo groups will be compared for *hypotension associated with organ dysfunction* within the first 5 days after study entry. *Hypotension associated with organ dysfunction* is defined as hypotension plus concomitant or subsequent organ dysfunction. Organ dysfunction in this setting is a composite outcome consisting of items 5a-5f (excluding item 5b4) of the secondary outcome of *clinical organ failure and serious infections* (section 4.1.2 of the TESICO master protocol). The composite outcome will be assessed on Day 5, and compared between treatment groups using CMH tests, stratified by

disease severity at baseline; the ORs will be estimated with 95% CIs using logistic regression, adjusted for disease severity at baseline.

8 Efficacy Analyses

Analysis cohorts: Separate efficacy analyses will be conducted for the **Aviptadil** cohort (comparison of aviptadil versus placebo), and the **Remdesivir** cohort (comparison of remdesivir versus placebo). Interactions between aviptadil and remdesivir will be assessed in the **Factorial** cohort (assessment whether the effects of aviptadil and remdesivir are independent of each other, section 9).

Efficacy analyses will be by intention-to-treat, unless otherwise stated.

8.1 Primary Efficacy Endpoint

The **primary endpoint** of the trial is a 6-category ordinal outcome that assesses the participants' recovery status at Day 90, referred to "recovery". The six ordered categories of recovery are shown in Table 1 below; they consist of 3 ranked categories that describe the number of days alive, at home, and not receiving new supplemental oxygen **at Day 90** (77 or more consecutive days, 49–76 days, or 1–48 days) as well as an additional 3 categories for patients who are not recovered at Day 90. The ranking is from 1=best to 6=worst (death).

Table 1. Categories of the primary endpoint of recovery at Day 90

Category	Status at 90 days
1 (Best)	At home and off oxygen. No. of consecutive days at Day 90 ≥ 77
2	49–76
3	1–48
4	Not hospitalized AND either at home on oxygen OR not at home
5	Hospitalized for medical care OR in hospice care
6 (Worst)	Dead

Definition of **Home** for the primary endpoint:

According to the protocol, section 4.1, and consistent with the TICO protocol (NCT04501978), **Home** is defined as the level of residence or facility where the participant was residing prior to hospital admission leading to enrollment in this protocol.

Residence or facility groupings to define home are:

- 1) **Independent/community dwelling** with or without help, including house, apartment, undomiciled/homeless, shelter, or hotel

- 2) **Residential care facility** (e.g., assisted living facility, group home, other non-medical institutional setting)
- 3) **Other healthcare facility** (e.g., skilled nursing facility, acute rehab facility)
- 4) **Long-term acute care hospital** (hospital aimed at providing intensive, longer term acute care services, often for more than 28 days).

Lower (less intensive) level of residence or facility will also be considered as home. By definition, “home” cannot be a “short-term acute care” facility. Participants previously residing in a “long-term acute care” hospital recover when they return to the same or lower level of care.

Participants residing in a facility solely for public health or quarantine purposes will be considered as residing in the lowest level of required residence had these public health measures not been instated.

Since some patients may have been receiving supplemental oxygen before their COVID-19 illness, we define **new supplemental oxygen** as any supplemental oxygen in participants who were not receiving supplemental oxygen before their COVID-19 illness or an increase in supplemental oxygen above pre-COVID-19 baseline among patients who were receiving supplemental oxygen before their COVID-19.

The “**last-off**” method for assessing recovery will be used, as has been customary in the use of similar ordinal endpoints in ARDS trials for decades. According to the “last-off” method, periods of recovery that are followed by hospital re-admission, change from home to a higher level of care, or receipt of new supplemental oxygen will *not be counted* toward the number of days of recovery. In other words, only days between the last time the patient entered a recovered state (returned home, free of new supplemental oxygen), and Day 90 are counted as days of recovery.

